4.2. DETAILED STUDY PROCEDURES

For the purpose of the study, time period prior to study drug is defined as 12 hours prior to initiation to 30 minutes prior to initiation of study drug. Baseline is defined as the period 30 min prior to initiation of study drug. The monitoring period is defined as the period of study drug infusion and the first 24-hours following study drug cessation.

4.2.1. Screening

All mothers and infants with an antenatal or postnatal diagnosis of CDH will be included in screening.

The screening log will include – confirmation of gestational age, birth weight and antenatal or postnatal diagnosis of CDH.

4.2.2. Consent Procedures

Mothers with an antenatal diagnosis of fetal CDH and infants admitted with a postnatal diagnosis of CDH will be screened and approached for consent.

- (i) In many institutions, mothers are referred by the Obstetrician and/or Maternal-Fetal Medicine (MFM) specialist for a consult with Pediatric Surgery and Neonatology. This would be an ideal time to obtain consent (brochures for distribution and consenting will be provided to all centers).
- (ii) Mothers admitted to labor and delivery with an antenatal diagnosis may be approached for consent (if not in active labor or on narcotic analgesia).
- (iii) Infants that are diagnosed postnatally, or born to mothers that could not be consented during the prenatal period or transferred from outside hospitals may be approached in the first 168 hours of life (7 days).
- (iv) Permission to access maternal records to record antenatal glucocorticoid therapy, ultrasound and MRI based assessment of severity of CDH will be requested at the time of consent (included in the consent form).

- (v) Permission to access infant's records from providers (subsequent hospitalizations, pediatric primary care providers and subspecialty consultants to obtain follow-up information until the baby's first birthday will be requested at the time of consent (included in the consent form).

4.2.3. Randomization Procedures

The following information must be checked and/or confirmed prior to randomization. (a) chest X-ray to confirm the presence of unilateral CDH, (b) complete blood count – CBC to check platelet count and (c) a blood gas – arterial, venous or capillary to document a $\text{PCO}_2 \leq 80 \text{ mm Hg}$. These labs are routinely obtained to evaluate babies with suspected CDH in most institutions. Data from a baseline echocardiogram prior to initiation of study drug (if obtained for clinical purposes) is recorded but is not necessary for randomization (see 4.1.2 (5) above).

- (i) The diagnosis of CDH and the side of the defect must be confirmed with a chest X-ray.
- (ii) Adequate platelet count ($\geq 80,000/\text{mm}^3$) on the most recent CBC (after a platelet transfusion if necessary).
- (iii) Optional - An indwelling arterial line is placed (if not available oxygen saturation index or OSI is collected).
- (iv) Concurrent, ongoing therapy with a parenteral (IV/SQ) pulmonary vasodilator (milrinone, epoprostenol, treprostинil or sildenafil) is a contraindication to the study.
- (v) An arterial blood gas (preductal or postductal) with an oxygenation index of ≥ 10 (or OSI ≥ 5 in the absence of an arterial blood gas) and an arterial, venous or capillary blood gas with $\text{PCO}_2 \leq 80 \text{ mmHg}$ on the most recent blood gas (or pulse oximeter recording) should be recorded within 12 hours prior to randomization. An acute reversible mechanical factor such as endotracheal tube obstruction as a cause of elevated OI should be ruled out prior to randomization. If both preductal and postductal gases are available (this is rare), a preference is given to preductal – right radial or ulnar arterial draws, for calculation of OI. (Gien and Kinsella 2016) The same site (preductal or postductal) must be used at various time points for consistent comparison.
- (vi) Infants with CDH are eligible for enrollment if there are no exclusions and the most recent blood gas drawn within 12 hours prior to randomization has an OI ≥ 10 .
 - a. In patients without arterial access and/or an arterial blood gas, oxygen saturation index (OSI) can be calculated and if ≥ 5 , randomization can be performed.

(vii) Once the infant meets these eligibility criteria and is randomized, the study drug infusion should start within 5 hours of randomization (if not, a protocol deviation form should be filled out). Once the infant is randomized, study drug is initiated even if a subsequent blood gas obtained for clinical purposes has an OI < 10 (or OSI is < 5 if there is no arterial blood gas).

Eligible infants will be randomized to either milrinone arm or placebo arm using a phone or web system in a 1:1 ratio.

4.2.4. Stratification:

Patients will be stratified based on the severity of HRF using the prediction formula (PaO₂/FiO₂ ratio – PaCO₂ value) at the time of randomization. Patients with prediction value ≥ 0 will be considered as “moderate” and infants with a value of < 0 as “severe” HRF. If arterial line is not present prior to randomization, preductal OSI value of 5 to 10 (moderate) and > 10 (severe) will be used to determine severity of respiratory failure.

In addition, side of the defect, center, prenatal (observed to expected lung to head ratio – LHR, position of the liver, lung volume assessment by MRI) (Ruano, Lazar et al. 2014), postnatal (OI (Ruttenstock, Wright et al. 2015), oxygen saturation index = mean airway pressure x FiO₂ x 100 \div preductal SpO₂) (Rawat, Chandrasekharan et al. 2015) (Park, Lee et al. 2013), evidence of pulmonary hypertension (velocity of the tricuspid regurgitation jet – if present, the position of the inter-ventricular septum and direction of shunt at the patent foramen ovale – PFO and patent ductus arteriosus – PDA level) and intraoperative (defect size) (Congenital Diaphragmatic Hernia Study, Lally et al. 2007) markers of disease severity will be recorded (but not used for stratification).

4.2.5 In-hospital Procedures

Pharmacy: Once the randomization code is received, the study pharmacist at the center will prepare an infusion of milrinone (pre-mixed bags contain 200 μ g/mL of milrinone are preferred and do not need any further reconstitution in the pharmacy; Milrinone is also available in 1 mg/mL solution for injection as 10-, 20-, and 50-mL single dose vials). **Only FDA approved milrinone products will be used in this study.** Infusion is initiated at 0.33 μ g/kg/min (20 μ g/kg/h; about 0.1 ml/kg/h) after priming the infusion circuit. An equivalent volume of 5% dextrose (D5W) will be used for infants randomized to the placebo arm. The premix solution in D5W has a pH of 3.2 to 4.0. Milrinone solution prepared from a single-dose vial is stable for 24

hours. The ready-to-use 200 µg/ml pre-mix solution is stable for a longer period of time if no further dilution/alterations are done.

Although 0.9% saline, 0.45% saline and dextrose 5% can be used as diluents, only dilution with dextrose 5% solution is permitted. This is necessary to maintain similarity to premix bags and placebo (also dextrose 5% solution).

Approximate time for compounding at the pharmacy using premixed solution on weekdays during daytime is approximately 30 min and during weekends and nights is 60-75 min based on staffing (data from Women and Children's Hospital of Buffalo). A maximum duration of 5 hours is permitted between randomization and initiation of study drug. Failure to initiate study drug within this time frame is a protocol deviation.

Dose: Milrinone/placebo will be initiated an infusion of 0.33 µg/kg/min (or 20 µg/kg/h or 0.1 ml/kg/h of pre-mixed 200 µg/ml solution). It is recommended that infants receive a fluid bolus (Lactated Ringers solution - preferred or 0.9% normal saline 10 mL/kg) *before* initiating study drug to avoid systemic hypotension, unless there is a contraindication. If after 120 min of infusion of this dose of study drug (and within 240 min of study drug initiation), no evidence of hypotension (defined as mean blood pressure < 35 mmHg for at least 30 minutes) and a vasoactive inotrope score ≤ 30 (see below for calculation of vasoactive inotrope score) , the rate of the study drug infusion is increased to 0.66 µg/kg/min (40 µg/kg/h or 0.2 ml/kg/h of pre-mixed solution).

Compatibility: Milrinone is compatible with D5W, normal saline and Lactated Ringers solution. Milrinone is incompatible with furosemide, imipenem/cilastatin and procainamide.

Vasoactive Inotrope score:

A vasoactive inotrope score is a quantitative assessment of the degree of therapeutic support required by the patient to maintain adequate perfusion and/or blood pressure. It is calculated by the following equation (Rosenzweig, Starc et al. 1999, Kumar, Sharma et al. 2014, Maeda, Toda et al. 2015) (Gaines, Gurney et al. 2010):

Inotrope score = dose of dopamine in µg/kg/min + dose of dobutamine in µg/kg/min + 100 X epinephrine dose in µg/kg/min + 100 X norepinephrine dose in µg/kg/min + 100 X phenylephrine dose in µg/kg/min) + vasopressin dose (U/kg/min x 10000)

Note – the original formula includes 10 x milrinone dose (µg/kg/min). This has been excluded as patients will not be on open-label milrinone while on study drug infusion.

[figure not shown]

Figure 6. Initiation, maintenance and weaning of study drug (black line) in relation to oxygenation index (OI – orange shaded area). The study infusion is initiated at $0.33 \mu\text{g}/\text{kg}/\text{min}$ when $\text{OI} \geq 10$. The dose is escalated to $0.66 \mu\text{g}/\text{kg}/\text{min}$ 2 to 4 h later if there are no adverse effects (mean BP < 35 mmHg and vasoactive inotrope score of > 30). The dose is maintained at $0.66 \mu\text{g}/\text{kg}/\text{min}$ for the duration of the study. The study drug is weaned to $0.33 \mu\text{g}/\text{kg}/\text{min}$ at 70h of infusion or if $\text{OI} < 7$ on two consecutive blood gases at least an hour apart (whichever time point is earlier). Two hours after the first wean, the study drug must be stopped. Study drug is also stopped if there is a severe or life-threatening adverse event (hypotension, hemorrhage, arrhythmia or renal dysfunction)

Management of the patient:

Management of the infant with CDH is completely based on center protocols or as per individual physician. The reference list includes publications on guidelines for CDH management

from the European consortium.(Reiss, Schaible et al. 2010) (Snoek, Capolupo et al. 2014, Snoek, Reiss et al. 2016)

If the patient is found to have any of the following criteria during the course of therapy, the study drug should be discontinued as described below.

- (i) Diagnosed with severe or life-threatening intracranial bleed/echodensity as defined in the MOP
- (ii) Diagnosed with severe or life-threatening renal dysfunction as defined in the MOP
- (iii) Diagnosed with severe or life-threatening arrhythmia as defined in the MOP not attributed to other causes such as electrolyte disturbances or a central line in the right atrium
- (iv) Diagnosed with severe or life-threatening intracranial bleed as defined in the MOP
- (v) Confirmed trisomy 13 or 18 by chromosomal analysis

Note: Respiratory deterioration is common in the natural history of CDH and should not be a reason for discontinuing study drug.

Duration of study intervention

In the absence of complications:

- (i) Milrinone/placebo is continued until oxygenation improves and two OIs obtained at least one hour apart are less than 7 (OSI < 3.5, if no arterial blood gas is available), then weaned according to the protocol below, or
- (ii) Milrinone/placebo is weaned and discontinued after a maximum of 3 days of therapy (72 hours from the initiation).

Surgery and ECMO:

- (i) Milrinone/placebo should preferably be continued if the patient requires ECMO irrespective of the mode of ECMO – VA vs. VV (Reason: although pharmacokinetics and volume of distribution are altered, milrinone may be beneficial with improved cardiac function especially during VV ECMO). (Note: ECMO use varies from center to center, but averages around 30%. This will mean that a fair number of the high risk patients are excluded unless they are enrolled soon after birth)
- (ii) It is recommended that the study drug be continued through surgery. If the surgical team prefers to discontinue the study drug, this indication should be recorded and study drug weaned as per protocol.

(iii) Note: if the clinical team decides to wean the baby off the study drug prior to ECMO or surgery, these reasons are documented as indications for discontinuing the study drug. It is not considered a protocol deviation or violation to wean the medication prior to surgery or ECMO. If serious, potentially drug-related complications occur, drug should be discontinued immediately (without weaning).

Study drug discontinuation criteria:

Milrinone/placebo is discontinued (without weaning) if the patient develops 'severe' or 'life-threatening' hypotension, intracranial or extracranial hemorrhage, renal dysfunction or arrhythmia that cannot be attributed to other causes.

Note:

The study drug can be discontinued (with or without weaning) by the clinical team at any time point if the team is concerned that the study drug poses a risk to the infant. An indication for discontinuation should be recorded. The reason for discontinuation of study drug i.e., (a) due to completion of 72 h of infusion, (b) due to achievement of improved oxygenation (OI < 7 or OSI < 3.5, if no arterial blood gas is available), (c) secondary to occurrence of a side effect (intractable hypotension, intracranial hemorrhage, arrhythmia or renal dysfunction) or (d) due to a decision of the clinical team is recorded.

Weaning of study drug (figure 6):

(i) Once discontinuation criteria are reached, milrinone/placebo is weaned by 0.33 µg/kg/min every two hours and discontinued (total duration of wean 2 h if the patient is on 0.66 µg/kg/min and abrupt cessation of the medication infusion if the patient is on 0.33 µg/kg/min). If the subject is on 0.66 µg/kg/min, weaning is initiated at 70 hours after initiation of study drug. If the subject is on 0.33 µg/kg/min, no weaning is required and the study drug is stopped at 72 hours after initiation. NOTE: Once discontinuation criteria are reached and weaning is initiated, the study drug is discontinued after the wean. If the study drug is not weaned within 4 hours of meeting discontinuation criteria, this is considered a protocol deviation. If the wean was initiated following two OI values of < 7 (or OSI of < 3.5) and oxygenation worsens after initiating the wean, the study drug should still be discontinued as the end-point was met. However, open-label milrinone can be started soon after discontinuation of the study drug.

- (ii) If adverse events such as severe or life-threatening hypotension, intracranial or extracranial bleed,, arrhythmia or renal dysfunction are observed, study drug is abruptly stopped without gradual weaning.

Open-label milrinone use:

Immediately after completion of study intervention, open-label milrinone is permitted at the discretion of the clinical team. The study drug infusion will be 0.33 µg/kg/min at the time of cessation if gradual weaning protocol is adopted. It is recommended that the clinical team start open-label milrinone at this rate and adjust the dose based on clinical response. If the clinical team initiates open-label milrinone at 0.33 mcg/kg/min immediately after weaning the study drug, there is no discontinuity in therapy (for patients in the milrinone arm).

Criteria for re-initiation of study drug:

After the patient has met criteria for study drug discontinuation once (due to improvement in oxygenation and meeting OI criteria, or due to side effects such as severe hypotension, intracranial bleeding or renal dysfunction), study drug is discontinued and cannot be reinitiated even if the indication for initial discontinuation is resolved (for e.g., OI exceeds 10 after cessation of study drug or hypotension is resolved and blood pressure is normal etc.,). The clinical team may start open-label milrinone.

During the post-study drug infusion period, data regarding open-label milrinone use, pressor use, and vasodilator use will be recorded for 24 hours after cessation of study-drug.

Fluid intake:

- (i) As systemic hypotension and fluid bolus administration are common in patients with CDH and PPHN, it is important to record daily fluid intake.
- (ii) Total fluid intake (including maintenance fluids/TPN, flushes, medications, boluses and blood products) will be recorded for three 24-hour periods as entered in the nursing notes/EMR (please see MOP for details).

Clinical criteria for ECMO:

The decision to place an infant with CDH on ECMO is ***entirely up to the clinical team***. Many centers prefer to use ECMO for preoperative stabilization. The following general guidelines are provided as criteria for ECMO (Reiss, Schaible et al. 2010) (Snoek, Reiss et al. 2016):

- (i) Oxygenation index is consistently ≥ 40 for at least 3 h and/or
- (ii) Inability to maintain preductal saturations $> 85\%$ or postductal saturations $> 70\%$ and/or
- (iii) Increased PaCO_2 and respiratory acidosis with $\text{pH} < 7.15$ despite optimization of ventilator management and/or
- (iv) $\text{PIP} > 28 \text{ cm H}_2\text{O}$ or mean airway pressure $> 17 \text{ cm H}_2\text{O}$ is required to achieve saturations $> 85\%$ and $\text{PaCO}_2 < 65 \text{ mmHg}$ and/or
- (v) Inadequate oxygen delivery with metabolic acidosis as measured by elevated lactate $\geq 5 \text{ mM/L}$ and $\text{pH} < 7.15$ and/or
- (vi) Systemic hypotension (mean blood pressure $< 30 \text{ mmHg}$), resistant to fluid and inotropic support, resulting in hypoperfusion and/or oliguria (urine output $< 0.5 \text{ mL/kg/h}$) for at least 12-24h

Subject specimens: Information about blood counts, imaging and blood gases will be obtained from blood draws conducted for the purpose of clinical care. No additional blood work will be performed for the purpose of research.

Echocardiography: Data from a maximum of 4 clinical echocardiograms will be recorded. No additional echocardiograms will be performed for the purpose of this study. To estimate the secondary outcome of improvement in cardiac function and pulmonary hypertension, data from at least two echocardiograms will be obtained if available – the first echocardiogram preferably prior to initiation of the study drug. If echocardiogram is not performed prior to study drug initiation, study drug may be initiated.

If clinical echocardiograms are obtained during the study drug infusion, data from the clinical echocardiogram closest to 24 hours after study drug infusion is used to calculate the secondary outcome of change in echocardiographic findings. If a third echocardiogram is obtained close to 72 hours after initiation of study drug, data from this study will be recorded. In addition, data from any other echocardiograms obtained for clinical purposes after completion of study drug will be recorded (maximum of 4 echocardiograms).

Cranial ultrasound: As mentioned previously, an initial cranial ultrasound is obtained prior to initiation of study drug or within 4 hours of commencement of the study drug. A second cranial ultrasound is obtained preferably within 24 hours (maximum within 96 hours) of completion of the study drug. Both these cranial ultrasounds are covered by the study budget. Additional head imaging may be performed based on clinical indications but are not covered by the study budget. If the patient has a screening ultrasound that demonstrates intracranial hemorrhage

(as outlined in the exclusion criteria) prior to starting the study-drug, the patient is not randomized. In this case, only one screening cranial ultrasound is covered by the study budget.

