- use of milrinone infusion prior to randomization (the use of other inhaled pulmonary vasodilators such as iNO, inhaled epoprostenol, inhaled treprostинil, inhaled PGE1 and oral such as endothelin receptor antagonists is permitted – Note: it is unlikely to be on oral pulmonary vasodilators early in the course of CDH)
- ongoing therapy with parenteral (intravenous or subcutaneous) pulmonary vasodilators such as IV/SQ prostacyclin analogs (Epoprostenol – Flolan® or Treprostинil – Remodulin®) or IV phosphodiesterase 5 inhibitors (sildenafil – Revatio®) at the time of randomization. Administration of IPGE1 is not an exclusion criteria. In addition, initiation of therapy with these two classes of parenteral medications (except IPGE1) during the first 24 hours of study drug initiation is not permitted and will be considered a protocol deviation. The risk of systemic hypotension is high during the first 24 hours of study-drug (milrinone) infusion and hence parenteral administration of other pulmonary vasodilators is avoided to minimize risk of hypotension.
- Subjects already on ECMO or patients who are being actively considered for ECMO by the neonatal or surgical team
- Infants with hypoxic-ischemic encephalopathy (HIE) undergoing therapeutic hypothermia
- attending (neonatal, critical care or surgical) refusal for participation in the trial (including concern about presence of hemodynamic instability)

Study Intervention/Methods: An initial cranial ultrasound is obtained prior to initiation of study drug or within 4 hours of commencement of the study drug. A second cranial ultrasound is obtained preferably within 24 hours (maximum - within 96 hours) of completion of the study drug. Both these cranial ultrasounds are covered by the study budget. Additional head imaging may be performed based on clinical indications (but are not covered by the study budget). An echocardiogram, if clinically indicated, **will preferably** be obtained prior to (or within 6 hours of) initiation of the study drug. Infants with CDH will be randomized to receive a milrinone infusion at 0.33 μ g/kg/min or equal volume of placebo (D5W) infusion. The dose of the study drug will be increased to 0.66 μ g/kg/min 2 to 4 hours after initiation of study drug if there is no evidence of hypotension (as defined as mean blood pressure < 35 mmHg and a vasoactive

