inotrope score > 30; Vasoactive Inotrope score = dose of dopamine in $\mu\text{g}/\text{kg}/\text{min}$ + dose of dobutamine in $\mu\text{g}/\text{kg}/\text{min}$ + 100 X epinephrine dose in $\mu\text{g}/\text{kg}/\text{min}$ + 100 X norepinephrine dose in $\mu\text{g}/\text{kg}/\text{min}$ + 100 X phenylephrine dose in $\mu\text{g}/\text{kg}/\text{min}$ + 10000 x vasopressin dose in $\text{U}/\text{kg}/\text{min}$) two hours after initiation of study drug. Infusion will be continued until the OI decreases to < 7 (or OSI < 3.5 if no arterial blood gas is available). The study drug will be continued during surgery and if the patient requires either veno-arterial or veno-venous extracorporeal membrane oxygenation (VV-ECMO or VA-ECMO) if permitted by the clinical team. The maximum duration of study drug infusion is 72 h. After 70 h (if the patient is on 0.66 $\mu\text{g}/\text{kg}/\text{min}$ or 72h if the patient is on 0.33 $\mu\text{g}/\text{kg}/\text{min}$) of study drug infusion (or earlier if two consecutive OIs at least one hour apart are < 7 or OSIs < 3.5 if no arterial blood gas is available), the infusion rate of the study drug is weaned and subsequently discontinued. Data from a maximum of 4 echocardiograms, **if performed for clinical indications will be recorded**, (a) first echocardiogram, preferably prior to onset of study drug or within 6 hours of initiation of study drug, (b) second echocardiogram, 6 – 36 h after initiation of study medication (c) third echocardiogram, 36 h after initiation of study medication but prior to completion or discontinuation of study-drug and (d) first echocardiogram after completion of the study drug.

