Infusion of the study drug will be stopped if the mean blood pressure decreases < 35 mmHg and by > 20 mmHg (from pre-study drug mean blood pressure) after initiation of study drug and remains low for 2 hours despite treatment with > 40 ml/kg/24h of fluids and vasoactive medications (with a vasoactive inotrope score of > 30). Once the study drug is discontinued for improvement in oxygenation or a decrease in systemic blood pressure, it will not be restarted even if the condition leading to discontinuation changes (such as change in oxygenation or blood pressure). However, clinical providers can initiate open-label milrinone at their discretion. Study drug will also be stopped in the presence of renal dysfunction and/or development of a large intracranial (intraventricular with distension of the ventricle or parenchymal) bleed/echodensity.

Primary Outcome:

The primary outcome is the oxygenation response, as determined by change in OI (or OSI if no arterial blood gas is available) at 24h after initiation of study drug. In patients that require ECMO or die prior to completion of 24h from the initiation of the study drug, the last OI (or OSI if no arterial blood gas is available) prior to initiation of ECMO or death will be used for analysis. In patients without an arterial line (or if the line is lost), oxygen saturation index (OSI) will be calculated using a preductal oximeter. (Rawat, Chandrasekharan et al. 2015)

Secondary outcomes:

- (i) Oxygenation response at 24 h after initiation of study drug assigning a minimum OI of 40 or OSI of 20 for subjects that need ECMO or die after initiation of study drug infusion but prior to 24h of study-drug infusion. In this analysis if the patient's OI is 30 (or OSI of 15) and is cannulated for ECMO due to hemodynamic instability, he/she will be assigned an OI of 40 (or OSI of 20). However, if the OI prior to ECMO is 47 (i.e., > 40), the higher number (47) will be used for analysis of this secondary outcome.
- (ii) Oxygenation index at 48 and 72 h after initiation of study drug (or OI/OSI at the time of initiation of ECMO or immediately prior to death, for infants placed on ECMO or died before these time points),

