3.5. POTENTIAL RISKS AND BENEFITS TO SUBJECTS

Infants with CDH represent a high-risk population with mortality ranging from 30 to 40%. Additional risks from the use of IV milrinone include systemic hypotension, intracranial hemorrhage (reported in critically ill neonates with PPHN) and arrhythmias (reported in adults). The anticipated benefit is improvement in oxygenation and reduced need for ECMO.

Systemic hypotension is commonly seen in patients with CDH. In recent studies 80-90% of patients with CDH required treatment with vasoactive medications. (Snoek, Capolupo et al. 2016) Patients will be closely monitored for systemic hypotension due to its association with increased right –to-left shunting and hypoxemia. Study drug will be discontinued in the presence of 'severe' or 'life-threatening' systemic hypotension as outlined in the MOP that cannot be explained by other causes (such as sepsis or pneumothorax) and described below.

- a. Severe hypotension:
 - decrement in mean BP > 20 to 30 mmHg compared to the most recent value during the period prior to study drug or at baseline OR
 - receiving extensive volume therapy (40 to 80 ml/kg during a 24-hour period of the study monitoring period: onset of study drug to 24 hours after discontinuation of study drug) OR
 - escalation of vasoactive inotrope score by 20 to 30 compared to the score at baseline
- b. Life-threatening hypotension:
 - Decrease in mean BP > 30 mmHg compared to the most recent value during the period prior to study drug or at baseline OR
 - receiving volume therapy (> 80 ml/kg during a 24-hour period of the study monitoring period: onset of study drug to 24 hours after discontinuation of study drug) OR
 - escalation of vasoactive inotrope score by > 30 compared to the score at baseline)

(i) Vasoactive inotrope score calculation (vasoactive inotrope score = dopamine dose ($\mu\text{g}/\text{kg}/\text{min}$) + dobutamine dose ($\mu\text{g}/\text{kg}/\text{min}$) + epinephrine dose ($\mu\text{g}/\text{kg}/\text{min} \times 100$) + norepinephrine dose ($\mu\text{g}/\text{kg}/\text{min} \times 100$) + phenylephrine dose ($\mu\text{g}/\text{kg}/\text{min} \times 100$) + vasopressin dose ($\text{U}/\text{kg}/\text{min} \times 10000$) (Gaies, Gurney et al. 2010)

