4.1.2. Exclusion Criteria

Infants are ineligible if they meet any of the following criteria:

- known hypertrophic cardiomyopathy
 - Note 1: infants of diabetic mothers with asymmetric septal hypertrophy can be included as long as there is no evidence of obstruction to left ventricular outflow tract on echocardiogram,

- Note 2: infants with other acyanotic congenital heart disease (CHD) and CDH may be included in the study and will be a predetermined subgroup for analysis)
- cyanotic CHD – transposition of great arteries (TGA), total anomalous pulmonary venous return (TAPVR), partial anomalous pulmonary venous return (PAPVR), truncus arteriosus (TA), tetralogy of Fallot (TOF), single ventricle physiology – hypoplastic left heart syndrome (HLHS), tricuspid atresia, critical pulmonic stenosis or atresia etc.,
- enrolled in conflicting clinical trials (such as a randomized controlled blinded trial of another pulmonary vasodilator therapy); Note: mothers enrolled in fetal tracheal occlusion studies such as FETO may be enrolled if permitted by investigators of the fetal tracheal occlusion study; More information about FETO can be found at <http://www.chop.edu/centers-programs/center-fetal-diagnosis-and-treatment/fetoscopic-endoluminal-tracheal-occlusion-feto> or <http://childrens.memorialhermann.org/FETO-trial/> [FETO refers to fetoscopic endoluminal tracheal occlusion and involves occlusion of fetal trachea with a balloon device at mid-gestation and subsequent removal in later gestation]
- infants with bilateral CDH
 - Note 3: infants with anterior and central defects are included in the study
- associated abnormalities of the trachea or esophagus (trachea-esophageal fistula, esophageal atresia, laryngeal web, tracheal agenesis)
- renal dysfunction (with serum creatinine > 2 mg/dL not due to maternal factors) or oligohydramnios associated with renal dysfunction at randomization; renal dysfunction may be secondary to renal anomalies or medical conditions such as acute tubular necrosis
- systemic hypotension (mean blood pressure < 35 mm Hg for at least 2 h with a vasoactive inotrope score of > 30)
- decision is made to provide comfort/ palliative care and not full treatment
- Known intracranial bleed (including the following descriptions on the cranial ultrasound)
 - Parenchymal hemorrhage – including blood in the cerebral parenchyma, cerebellar parenchyma or basal ganglia
 - Blood/echodensity in the ventricle with distension of the ventricle

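### The rule for doubling the study drug at 2 to 4 hours is worded two ways, and on its natural reading the summary is more permissive than section 4.2.5

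*Combined protocol and SAP*

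**What the plan says.** The increase is described in three places.

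- **Section 4.2.5, Dose.** Between 120 and 240 minutes after the start, the rate is raised if there is "no evidence of hypotension (defined as mean blood pressure < 35 mmHg for at least 30 minutes) and a vasoactive inotrope score" of 30 or less. Hypotension is defined by pressure and duration alone, and the score is a separate requirement.
- **Protocol summary, Study Intervention/Methods.** In the same 2 to 4 hour window the dose is raised "if there is no evidence of hypotension (as defined as mean blood pressure < 35 mmHg and a vasoactive", and the sentence continues "inotrope score > 30; Vasoactive Inotrope score = dose of dopamine in" (the score formula follows). Both findings sit in one defining parenthesis. No duration is given.
- **Section 4.2.5, Figure 6 legend.** The dose goes up "2 to 4 h later if there are no adverse effects (mean BP < 35 mmHg and vasoactive inotrope score of > 30". This too gives no duration.

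No text says which wording governs. Sections 3.5 and 4.2.5 refer to the MOP for operational definitions, but it is not among the documents.

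**The concern.** The rule is a safety limit on doubling a vasodilator (0.66 / 0.33 = 2). Section 4.1.2 says the risk of hypotension is high in the first 24 hours of infusion. Section 2.3.3 says that neonates given no loading dose have reached only half of steady state by 2 hours, so exposure to the starting dose is still rising when the decision is made.

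A site working from the summary, read naturally, would double the dose in an infant whose mean pressure has been below 35 mmHg for half an hour or more on modest vasoactive support. A site working from 4.2.5 would hold. At stake are the safety limit itself and consistent dosing across sites.

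**Working it through.** The plan gives no figure to reproduce. The check is a comparison of rules.

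**1. The rules as logic**

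- Section 4.2.5: hold if mean BP < 35 mmHg for at least 30 minutes, or score > 30.
- Summary, joint reading: hold only if mean BP < 35 mmHg and score > 30.
- Summary, list reading: hold if mean BP < 35 mmHg for any duration, or score > 30.

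**2. All combinations** (3 pressure states × 2 score states = 6)

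| State | Mean BP (mmHg) | Score | 4.2.5 | Summary, joint | Summary, list |
|---|---|---|---|---|---|
| 1 | ≥ 35 | ≤ 30 | increase | increase | increase |
| 2 | ≥ 35 | > 30 | hold | **increase** | hold |
| 3 | < 35, under 30 min | ≤ 30 | increase | increase | **hold** |
| 4 | < 35, under 30 min | > 30 | hold | hold | hold |
| 5 | < 35, 30 min or more | ≤ 30 | hold | **increase** | hold |
| 6 | < 35, 30 min or more | > 30 | hold | hold | hold |

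On the joint reading the summary departs from 4.2.5 in states 2 and 5 (2 of 6), each time by increasing where 4.2.5 holds. On the list reading it departs only in state 3 (1 of 6), where it is the stricter text, and the sole cause is the missing 30 minutes. The Figure 6 legend gives the same two patterns, depending on how it is read.

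**3. Do the stopping rules cover state 5?**

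The summary stops drug when pressure is low and has also fallen enough, "Infusion of the study drug will be stopped if the mean blood pressure decreases < 35 mmHg and by > 20 mmHg", and stays low for 2 hours despite more than 40 ml/kg/24 h of "fluids and vasoactive medications (with a vasoactive inotrope score of > 30". Section 3.5 defines severe hypotension by any one of three limbs: "decrement in mean BP > 20 to 30 mmHg compared to the most recent value during the period prior to study drug"; volume of 40 ml/kg or more in 24 hours; or a score rise of 20 or more.

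The pressure limb needs a fall of more than 20 mmHg. At a current mean BP of x it is unmet for any pre-drug value up to x + 20:

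- x = 34: unmet up to 54
- x = 32: unmet up to 52
- x = 30: unmet up to 50

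An illustrative infant in state 5: mean BP 45 to 32 for 45 minutes (fall 45 − 32 = 13), score 10 to 15 (rise 5), 10 ml/kg given. No stop limb is met. Section 4.2.5 says hold, and the summary read jointly says increase.

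**4. Does eligibility remove these infants?**

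The exclusion in section 4.1.2 is "systemic hypotension (mean blood pressure < 35 mm Hg for at least 2 h with a vasoactive inotrope score of > 30", which needs both findings. An infant with only one of them stays eligible unless the attending refuses.

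**5. Do the other definitions show which rule was meant?**

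They point both ways. The section 4.1.2 exclusion and the summary stop rule combine low pressure with a high score. The severe-hypotension definitions in sections 3.5 and 5.5.3 link their limbs with OR.

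**The case against.** The best defence is that the summary is only a synopsis. Section 4.2 is headed as the detailed procedures, and its Dose paragraph is clear. If the summary's wording is a list of two grounds for holding, 4.2.5 merely supplies a duration that the synopsis left out, which is ordinary abbreviation. The legend's plural reference to adverse effects, followed by two items, leans towards a list. This stands in part: on the list reading what remains is small, and a reader should not infer that the texts clash seriously however they are read. It does not remove the point, because a definition that joins two findings is most naturally read as needing both. The legend, which lies inside 4.2.5, also lacks the duration.

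It is also fair that 2 of 6 counts logical states, not infants, and that in one of the two the pressure is at least 35 mmHg. Only state 5 carries the safety concern. There, the team's freedom in 4.2.5 to stop drug when worried is a real safeguard, although it does not say whether to increase or hold.

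A reader might infer that the sponsor meant the joint rule, or that sites would in fact dose differently. The documents show neither. The protocol's other definitions of hypotension are mixed, and the MOP may already settle the matter.

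**Conclusion.** The inconsistency holds and should be corrected. On the natural reading of the summary, the two rules differ in 2 of 6 states, with the summary more permissive in both. The state of concern is mean BP below 35 mmHg for 30 minutes or more with a score of 30 or less, and an infant there need not meet any stopping rule. This rests on the joint reading; on the list reading only the 30-minute duration is at issue.

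Two larger conclusions might be drawn, and the documents support neither. The first is bias: the rule applies identically to both masked arms, so the randomised comparison is not biased. The second is a count of infants harmed or wrongly dosed. The PPHN series in section 2.3.3 cannot supply one: one that started at 0.33 without a loading dose reported no hypotension, another reported a fall in pressure at 6 hours, and neither says how often these states occur at 2 to 4 hours. The finding concerns the wording of a safety rule and does not touch sample size or power.

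**What to change.** Adopt the Dose paragraph of section 4.2.5 as the single rule, since it is the more detailed and the more cautious text. Ask the sponsor to confirm that this is what was intended and that the MOP agrees. Then:

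- In the summary, replace the condition with that of 4.2.5, copied unchanged together with its 120 to 240 minute window.
- In the Figure 6 legend, state the adverse effects as: mean BP < 35 mmHg for at least 30 minutes, or vasoactive inotrope score > 30.

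Do not add a clause that an infant who fails the check stays at 0.33. Section 4.2.5 does not say whether reassessment within the window is allowed, and such a clause would be a new rule.

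The cost is a wording amendment and a check of the MOP, with no extra patients, tests or analyses and no change to the 4.2.5 thresholds. The downside is that, if the sponsor had meant the joint rule, some infants would stay at the lower dose. That is why intent should be confirmed first.
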